| combined | 21 | 6 | 0.7121396 | 3.263434 | 4.514503 7.485497 |
| diff | -3 | 1.38873 | | -5.906646 | -0.0933544 |
| Diff= mean (x) – mean (y) | | | | t = -2.1602 | |
| Ho: diff = 0 | | | | Degrees of freedom = 19 | |
| Ha: diff < 0 | | Ha: diff != 0 | | Ha: diff > 0 | |
| Pr(T < t) = 0.0219 | | Pr(T > t) = 0.0437 | | Pr(T > t) = 0.9781 | |

Statistical plan for analyzing at least the primary hypothesis:

The sample size is powered to detect small differences in NRS score. Because itch is subjective and varies daily, subjects will be asked to keep an itch diary every day. For each subject, we will plot their average itch scores over time before and after drug intervention. For each dosage group, we will use linear regression methods with mix effects (GLM, SAS) to track the change in itch in each of the groups from baseline. This study will provide the effect size, standard deviation and range of itch scores in EB patients in order to properly power a larger phase 2 trial. This study can detect large differences in itch scores should Serlopitant decrease itch from severe to low-none at 1 and 2 months. At the 3 month follow up, we will measure the durability and length of response.

Matrix showing procedure plan for each study visit:

| Schedule of Events for Phase 2 Serlopitant | | | | | | | |
|--|------------------|-----------------|------------------------------|----------------|----------------|----------------|----------------|
| | Screening period | | Treatment period | | | Follow up | |
| | Phone call | Visit 1 | | Visit 2 | Visit 3 | Phone call | Early Term |
| | Screening call | Screening visit | Determination of Eligibility | Month 1 | Month 2/EOT | Month 3 | |
| Examination | Day -60 to -30 | Day -44* to -1 | Months 6 to 0 | Day 30 ±14 | Day 60 ±14 | Day 90 ±14 | |
| Informed consent/ Photographic consent | | X | | | | | |
| Demographics | | X | | | | | |
| Medical history | | X | Review | | | | |
| Prior ^a & current medications | X | X | | X | X | X | X |
| Abbreviated physical examination | | X | | | X | | X |
| Vital signs | | X | | X | X | | X |
| Urine pregnancy test (UPT) ^b | | X | Review results | X | X | | X |
| Inclusion/exclusion criteria | X | X | | | | | |
| Blood samples for clinical laboratory tests ^c | | X ^c | Review results | X ^c | X ^c | | X ^c |
| Randomization | | | X ^h | | | | |
| NRS ^d & Stanford EB survey | | X | | X | X | X ^e | X |
| Photograph the affected area ^f | | X | | X | X | | X |

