| Dispense study medication | | | X ^h | X | | | |
| Dispense subject diary | | X | X ^h | X | X ^g | | |
| Review/collect diary with subject | | | | X | X | X | X |
| Review and record adverse events | | | | X | X | X | X |

Note: NRS = numeric rating score.

* Includes up to 30 day washout from prohibited medications. The study medication and diary dispensation are to occur no more than 1-2 weeks after Screening Visit.

- a: all medications taken within 30 days prior to screening.
- b: for females of child-bearing potential.
- c: all subjects: hematology, serum chemistry will be measured at Screening, Month 1, and Month 2/EOT or early termination (ET).
- d: NRS recorded by subject daily, using diary, from screening visit through the end of the study; NRS is included in the Stanford EB Itch survey.
- e: the Stanford EB survey will be administered over the phone by a member of the research staff.
- f: photographs taken only if patient has signed photography consent
- g: a return envelope will be provided for the patient to return the study diary to Stanford after the follow up phone call

| | Schedule of Events for Phase 2 Serlopitant | | | | | | |
|--|--|---------|------------------|---------|---------|------------|------------|
| | Screening period | | Treatment period | | | Follow up | |
| | Phone call | Visit 1 | | Visit 2 | Visit 3 | Phone call | Early Term |

h: Patient letter of enrollment and study medication will be mailed to patient after determination of eligibility following the Screening Visit

Each subject will be un-blinded individually after completing 3 months of study period. All patients who complete the study will be offered a 2-month trial on active drug. Patient who received active drug in the first phase will be contacted and asked if they would like to continue on active drug for an additional 2 months. Patients who received placebo in the first phase will be contacted and asked if they would like to repeat the study on open label for 2 months.

When this occurs, the schedule of events will be as follows:

Patients who would like to continue with the treatment for the open-label extension portion of the study will be provided with the research medication and research daily diary. They will be followed up by phone at baseline, 1 month, 2 months, and 3 months (wash out). In addition, they will go to an external lab near their home for lab monitoring that will occur once a month for the two months they are on active drug.

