Data Monitoring Plan:

The Principal Investigator will provide oversight on monitoring safety/AEs/SAEs at this site. While there is not Data Safety Monitoring Board, the PI will act as the medical expert who answers safety/medical questions and who will provide medical expert opinion on this study. All AEs will be regularly reviewed and evaluated. The investigator will assess whether the AE represents an unanticipated problem (UP). If the investigator determines that the AE represents a UP, the investigator will promptly report the AE to the IRB. If the adverse event does not qualify as a UP, the adverse event should be reported at continuing review.

FDA Reporting:

In this study, the occurrence of any SAE from the time of informed consent until 4 weeks after the last dose of study drug will be reported to the Stanford IRB and the FDA within 24 hours of coming to the attention of the investigator.

Reporting any unexpected fatal or life-threatening suspected adverse reactions to the FDA will occur no later than 7 calendar days after initial receipt of the information.

Reporting any serious, unexpected suspected adverse reactions, findings from other clinical, animal or in-vitro studies that suggest significant human risk, and (3) a clinically important increase in the rate of a serious suspected adverse reaction to the FDA and all investigators will occur no later than 15 calendar days after determining that the information qualifies for reporting.

Submission of annual progress reports will occur within 60 days of the anniversary of the date that the IND went into effect (date that clinical studies were permitted to begin).

9) Significance:

Management of chronic pruritus is notoriously challenging for patients with EB. In a comprehensive survey of 146 EB patients, itch was reported as the most bothersome EB symptom, ranking higher than acute or chronic pain or problems eating.¹ Furthermore, pruritus can induce an itch-scratch-blister cycle, which can exacerbate existing wounds or induce new wounds.² There have been no new drugs for chronic pruritus, and the current management of pruritus in EB with anti-histamines and topical steroids only minimally relieve itch.³

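### The adverse-event contact schedule does not guarantee a contact at or after the end of the protocol's own SAE window, and follow-up after early termination is unspecified

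*Combined protocol and SAP*

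**What the plan says.** The FDA Reporting text in section 8 requires any SAE occurring "from the time of informed consent until 4 weeks after the last dose of study drug" to be reported to the IRB and the FDA "within 24 hours of coming to the attention of the investigator".

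The Schedule of Events sets the contacts:

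- Consent is taken at the screening visit (Visit 1): "Informed consent/ Photographic consent | | X".
- The AE row reads "Review and record adverse events | | | | X | X | X | X". Against the column order "Phone call | Visit 1 | | Visit 2 | Visit 3 | Phone call | Early Term", the marks fall at Month 1, Month 2/EOT, the Month 3 call and Early Term. The screening call, Visit 1 and the eligibility step are blank.
- The last two scheduled contacts are placed at "Day 60 ±14 | Day 90 ±14". Both are counted in study days.
- A footnote limits the interval before treatment: "The study medication and diary dispensation are to occur no more than 1-2 weeks after Screening Visit".

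The Data Monitoring Plan adds that AEs will be reviewed regularly, but it describes no other way of collecting them. No text says what contact, if any, follows the Early Term visit.

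**The concern.** The reporting window is defined relative to the last dose, and the contacts are defined by study day. The two agree only when visits fall close to target. The 24-hour duty starts when the investigator learns of an event. A site that follows the grid exactly can therefore hold its last AE review before the four weeks are over, and after that it depends on subjects coming forward.

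Early terminators matter most here, because some may stop because of an adverse event. In the earlier chronic pruritus trial described in the background, five subjects (three of them on placebo) discontinued because of a treatment-emergent event.

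Safety is the first stated aim, drug is mailed to subjects, and there is no data safety monitoring board. The sample-size text gives 14 subjects in total and also groups of 7 and 14, which sum to 21. With either number, one unrecorded SAE would noticeably change the safety summary.

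**Working it through.** The plan gives no figure for the off-drug interval at the last AE review, so there is none to reproduce. The check is calendar arithmetic on the Schedule of Events, with 4 weeks taken as 28 days.

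**Inputs**

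- EOT visit: Day 60 ±14, so Day 46 to 74.
- Final call: Day 90 ±14, so Day 76 to 104.
- Month 1 visit: Day 30 ±14, so Day 16 to 44.
- Dispensing: at most 2 weeks (14 days) after the screening visit.

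**1. Gap from EOT to the final call, if dosing runs to the EOT visit**

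Let *a* and *b* be the deviations of the EOT visit and the call from target, each from −14 to +14.

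Gap = (90 + *b*) − (60 + *a*) = 30 + *b* − *a*

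- On target: 30 days, which is 2 days more than 28.
- Shortest: 76 − 74 = 2 days.
- Longest: 104 − 46 = 58 days.

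The gap is under 28 days when *a* − *b* is 3 or more. There are 29 × 29 = 841 permitted pairs. For each difference *d* from 3 to 28 there are 29 − *d* pairs, so the count is 26 + 25 + … + 1 = 26 × 27 / 2 = 351. As a share, 351 / 841 = 41.7%.

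Equivalently, a call on Day 90 reaches the end of the window only if the last dose was on or before Day 62 (90 − 28). A call on Day 76 does so only if it was on or before Day 48 (76 − 28).

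**2. Sensitivity: last dose on Day 60 whatever the visit date**

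The gap is 76 − 60 = 16 days at the shortest, 30 on target, and 104 − 60 = 44 at the longest. It can still fall below 28.

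**3. Early termination**

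If the Early Term visit is on the day of the last dose, none of the following 28 days is followed by a specified AE contact. If the visit is *k* days after the last dose (*k* below 28), the last 28 − *k* days are not.

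**4. Consent to the first marked AE review**

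Taking Day 0 as dispensing, the footnote puts consent no more than 14 days earlier. The longest interval is 14 + 44 = 58 days.

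**5. Feasibility of the remedy**

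Last dose plus 28 days falls on Day 74, 88 or 102 for a last dose on Day 46, 60 or 74. All three precede the current upper limit of Day 104.

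**The case against.** Several points on the other side stand.

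- **The target schedule works.** A reader might infer that the schedule fails to cover the window altogether. It does not: visits on target leave 30 days. What is missing is a guarantee.
- **The FDA Reporting text is a reporting rule triggered by awareness.** An event learned of by any route is reportable, whatever the grid shows. So the two texts do not strictly contradict each other. The gap is in active follow-up.
- **The 2-day figure is an extreme.** It needs the latest EOT visit, the earliest call and dosing up to the EOT visit. With a Day 60 last dose the minimum is 16 days. The 41.7% treats all day pairs alike and says nothing about how often sites will schedule that way; it is not a rate of missed follow-up.
- **Early terminators are not excluded from later contact.** A reader might infer from the last column that they receive none. The documents are silent: they neither provide the Month 3 call for these subjects nor rule it out.
- **The early interval can look longer than it is.** Taking the screening window back to Day −44 would give 88 days to the first AE review, but that ignores the 1–2 week dispensing limit, under which the maximum is 58. The Month 1 review can also collect earlier events retrospectively.
- **Extra AE marks before Month 1 are not well grounded.** Consent is signed at Visit 1, so a mark there adds little. The eligibility step has no visit or call attached and the drug is mailed, so a mark there would need a new contact for every subject.

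Completers are also contacted later about the open-label extension, and those who continue have a baseline call. No date relative to the last dose and no AE review is stated for that contact, so it does not close the gap.

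**Conclusion.** The point holds as a lack of guaranteed coverage. A site can comply with every window and still make its last AE review before the four weeks end: as little as 2 days off drug if dosing continues to EOT, or 16 days if the last dose is on Day 60. Of 841 permitted day combinations, 351 fall short of 28 days. After early termination no AE contact is specified, and whether the Month 3 call applies is left open.

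The delay of up to 58 days from consent to the first marked AE review is secondary. It mainly affects how promptly events are detected, and it assumes that study days are counted from dispensing. The 0-of-28-day reading for early terminators assumes that the visit falls on the last-dose day, which the documents do not state.

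This affects completeness of safety data and no efficacy inference. It is a cheap improvement.

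**What to change.** Reconcile the Schedule of Events with the FDA Reporting text:

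1. Keep the Month 3 call within Day 90 ±14, but require that the final AE review be no earlier than the end of the stated 4-week window, counted from the actual last dose. For last doses on Day 46 to 74 this can be met by Day 102.
2. State that early-termination subjects receive the same AE call, timed from their own last dose.
3. State that the Month 1 AE review collects events back to the date of consent.

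The cost is a change to the schedule wording and one phone call per early terminator. Some final calls move later: for an EOT visit and last dose on Day 74, the earliest call moves from Day 76 to Day 102, still inside the existing window. No additional visits are needed.
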